#### Analysis Plan:

The following variables will be evaluated as potential risk factors for MCA aneurysm formation: radii and cross-sectional area of the main MCA trunk ( $r_0$ ,  $p_0$ ) and its branches ( $r_1$ ,  $p_1$  and  $r_2$ ,  $p_2$  for the larger and smaller branch, respectively), tortuosity of MCA trunk, asymmetry ratio,  $r_2^2 r_1^{-2}$ , area ratio,  $(r_1^2+r_2^2)r_0^{-2}$ ,  $\Phi_1$  (°),  $\Phi_2$  (°),  $\alpha$  (°),  $V_m$  (cm/s), VFR (cm^3/s) and PI. Normal distribution of the study variables will be verified with Shapiro-Wilk test. The significance of intergroup and intragroup differences will be verified with Mann-Whitney U-

test and Wilcoxon signed-rank test, respectively. All morphological and hemodynamic parameters shown to differ significantly between the study groups will be subjected to logistic regression analysis with stepwise addition mode. The potential predictors of MCA aneurysm will be identified on univariate analysis, and the relationship between pairs of the significant predictors will be determined based on Pearson's linear correlation coefficients. The variables with *P*-values <0.1 on univariate analysis, except those being correlated with one another, will be included in multivariate logistic regression model, to identify independent predictors of MCA aneurysm. The results will be presented as odds ratios (ORs) and their 95% confidence intervals (CIs). The independent predictors of MCA aneurysm will be subjected to receiver operating characteristic (ROC) analysis to identify their cut-off values with optimal sensitivity and specificity. The results will be considered statistically significant for p-values <0.05. Statistical analyses will be performed with Statistica v.13.3 package (StatSoft, Tulsa, Oklahoma, USA).

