# 8. OUTCOME MEASURES

#### **Primary Outcome Measure:**

1. Computed tomography angiography (CTA) analysis of the cross-sectional area of the MCA bifurcations.

CTA scans in DICOM format will be used to create three-dimensional (3D) models of MCA bifurcation using Mimics Innovation Suite platform (Materialise, Leuven, Belgium). The points including the largest curvature of MCA main trunk and two post-bifurcations branches will be automatically calculated according to the centreline fitted with a computer-aided

design (CAD) tool. In these points the cross-sectional area (mm2) of the MCA trunk and its two post-bifurcation branches will be calculated automatically.

2. Computed tomography angiography (CTA) analysis of the best fit diameter of the MCA bifurcations.

CTA scans in DICOM format will be used to create three-dimensional (3D) models of MCA bifurcation using Mimics Innovation Suite platform (Materialise, Leuven, Belgium). The points including the largest curvature of MCA main trunk and two post-bifurcations branches will be automatically calculated according to the centreline fitted with a computer-aided design (CAD) tool. In these points the best fit diameter (mm) of the MCA trunk and its two post-bifurcation branches will be calculated automatically.

3. Computed tomography angiography (CTA) analysis of the angles between the MCA bifurcations components.

CTA scans in DICOM format will be used to create three-dimensional (3D) models of MCA bifurcation using Mimics Innovation Suite platform (Materialise, Leuven, Belgium). The points of the largest curvature of MCA main trunk and two post-bifurcations branches will be calculated according to the centreline fitted automatically with a computer-aided design (CAD) tool. The centrelines and the largest curvature points will be exported to 3-matic v.9.0 MIS software. Three points of the largest curvatures (the main MCA trunk and two post-bifurcations branches) together with the point of the intersection of both centrelines passing through the main trunk MCA and both branches will determine the arms and the apex of the three angles. The following angle values will be calculated automatically: the angle between the post-bifurcation branches ( $\alpha$  angle) and the angles between the MCA trunk and the larger and the smaller branches ( $\beta$  and  $\gamma$  angle).

4. Pulsatility Index (PI) as calculated from transcranial color-coded sonography (TCCS) blood flow velocities (cm/s)

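### Fifteen overlapping candidate predictors are screened at p<0.05 with no multiplicity control or exploratory label, so a study with no true predictor would still name one in roughly 22-37% of cases

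*Combined protocol and SAP*

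**What the plan says.** Section 7, Analysis Plan, opens the candidate list with "The following variables will be evaluated as potential risk factors for MCA aneurysm formation: radii and cross-sectional area of the main MCA trunk". It continues with the branch radii and areas, trunk tortuosity, two ratios, three angles, mean velocity, volume flow rate and pulsatility index.

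Selection then runs in stages:

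- **Group comparison** (Mann-Whitney between groups, Wilcoxon within): "All morphological and hemodynamic parameters shown to differ significantly between the study groups will be subjected to logistic regression analysis with stepwise addition mode".
- **Univariate screen and correlation filter**: variables with a P-value "<0.1 on univariate analysis, except those being correlated with one another, will be included in multivariate logistic regression model".
- **Final model**: survivors are called independent predictors, reported with odds ratios and 95% confidence intervals, and sent to ROC analysis for a cut-off.
- **Threshold for significance**: "The results will be considered statistically significant for p-values <0.05".

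Section 8 lists five items under Primary Outcome Measure without ranking them. Three hold several measurements each: areas ("In these points the cross-sectional area (mm2) of the MCA trunk and its two post-bifurcation branches will be calculated automatically"), diameters ("In these points the best fit diameter (mm) of the MCA trunk and its two post-bifurcation branches will be calculated automatically") and angles ("Computed tomography angiography (CTA) analysis of the angles between the MCA bifurcations components"). The other two are pulsatility index and volume flow rate.

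Neither section contains a multiplicity adjustment, a lead hypothesis, a validation step or an exploratory label. The Limitations paragraph does not raise the matter.

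**The concern.** The study's title and its Analysis Plan both aim at naming independent predictors. That claim is made if any one of 15 candidates survives, so the 5% level attached to each test is not the error rate of the claim. The screening and the final model use the same data, and the final P-values and confidence intervals take no account of the search. A chance finding would therefore be reported as an odds ratio, an interval and a cut-off, with nothing to tell the reader how many candidates were tried.

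**Working it through.** The documents give no family-wise error rate, power or sample-size derivation, so there is no figure of the plan's own to reproduce.

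**Counting the family** (Analysis Plan; Primary Outcome Measure)

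- Candidates: r0, p0, r1, p1, r2, p2, tortuosity, asymmetry ratio, area ratio, Φ1, Φ2, α, Vm, VFR, PI = 15.
- Primary measurements: 3 areas + 3 diameters + 3 angles + PI + VFR = 11.
- Mapping: r = d/2, Φ1 = 180 − β and Φ2 = 180 − γ, so 11 candidates correspond to the primary items. The other 15 − 11 = 4 (tortuosity, the two ratios, Vm) do not.

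**Reference values if tests were independent**, 1 − 0.95^k:

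| k | Chance of at least one p<0.05 |
|---|---|
| 5 | 22.6% |
| 9 | 37.0% |
| 11 | 43.1% |
| 15 | 53.7% |

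The candidates are not independent. The ratios are built from the radii, VFR = Vm × p0, and r and p describe the same three vessels. The pathway therefore has to be simulated.

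**Null simulation of the pathway**

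- From the documents: at least 75 cases and 75 controls (section 9), the formulas for ratios and VFR, Mann-Whitney p<0.05, univariate logistic P<0.1, correlation filter, multivariable p<0.05.
- Assumed: correlation between radii from 0 to 0.8, area measurement noise from 0 to 0.15 on the log scale, α from unrelated to strongly related to Φ1 + Φ2, variable scales, one case-control comparison per variable, and matching ignored.
- Runs: 1,500 per scenario in four scenarios. At a true rate of 0.33 the Monte Carlo standard error is √(0.33 × 0.67/1500) = 0.012.

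The plan does not say when two variables count as correlated, nor whether one of a correlated set is kept or all are dropped. Both readings were tried:

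| Result when no candidate is a true predictor | Share of studies |
|---|---|
| At least one Mann-Whitney p<0.05 | 39-45% |
| At least one final predictor, best of each correlated set kept | 30-37% |
| At least one final predictor, all mutually correlated variables dropped | 22-26% |

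Overall, 22-37% equals the false-positive rate of about 5 to 9 independent tests, and is 22/5 = 4.4 to 37/5 = 7.4 times the nominal 5%.

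**Effect and cost of adjustment**

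The smallest P-value must pass 0.05/15 = 0.0033 under Holm. In a null simulation with overlapping candidates, Holm gave a family-wise error of 2.8%.

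For power, take a normal variable with a difference of δ SD. The Mann-Whitney noncentrality is about δ × √(75/2) × √(3/π), and power is about Φ(noncentrality − z), with z = 1.960 unadjusted and 2.935 at 0.0033.

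- δ = 0.5: noncentrality 2.99. Unadjusted Φ(1.03) = 85%; at 0.0033, Φ(0.06) = 52%.
- δ = 0.7: noncentrality 4.19. Unadjusted Φ(2.23) = 99%; at 0.0033, Φ(1.25) = 90%.

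Simulation agrees: 84% to about 50% at 0.5 SD, and 99% to about 88-91% at 0.7 SD. With Benjamini-Hochberg the 0.5 SD figure is 50-66%, for 1 to 5 true predictors. The power simulations used 15 independent variables, so they only approximate the cost with overlapping ones.

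**The case against.** The strongest reply is that this is an observational study. Its stated objective is to analyse relationships, and the list is introduced as potential risk factors: "The following variables will be evaluated as potential risk factors for MCA aneurysm formation". No treatment decision or confirmatory hypothesis hangs on it. Unadjusted P-values with odds ratios, intervals and a plain caveat are a respectable choice in such work. This stands as an argument against making adjusted significance a hard gate for reporting. It does not cover the present text, which carries no caveat and gives survivors an unqualified name and a cut-off.

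A second reply is that Holm over 15 near-duplicates is conservative and costs power. That is true (2.8% against 5%). Collapsing the radius and area pairs, or naming one lead variable, would reduce the loss.

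A third is that section 2 lists the study as completed in June 2017. A change can therefore improve only the reporting and cannot restore prespecification.

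A reader might also infer more than the documents support:

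- **That the false-positive risk is 54%, or one in three as a fixed figure.** The first assumes independence, which the plan's own formulas rule out. The second depends on keeping the best of each correlated set, which the plan does not say.
- **That all 15 candidates sit under five co-primary outcomes.** Four do not, and the plan does not use the term co-primary.
- **That every step uses 0.05.** The univariate screen uses 0.1; only declared significance uses 0.05.

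**Conclusion.** The gap is real. Fifteen overlapping candidates feed a claim judged at p<0.05, with no multiplicity control and no exploratory label. With no true predictor, the plan would name at least one in roughly 22-37% of studies. That figure is not in the documents. It rests on a global null, 75 against 75, assumed correlations, one case-control comparison per variable, and either reading of the correlation filter. The Morphometric Analysis text defines four bifurcation groups, and the Analysis Plan does not say which comparison decides entry. If more than one counts, the rate could be higher; that case was not simulated. The documents do not support calling the design invalid or requiring adjusted significance before a result may be reported. This is an inexpensive improvement to how the claim is worded and supported.

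**What to change.** In section 7, Analysis Plan:

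1. Name the single case-control comparison per variable that forms the family of 15.
2. Report P-values for all 15 both unadjusted and adjusted, by Holm, or by Benjamini-Hochberg if a false-discovery claim is preferred.
3. Describe a variable as an independent predictor without qualification only if it is retained in the multivariable model and its adjusted P is <0.05. Both conditions are needed, because the adjusted P-values concern marginal tests and cannot alone show independence.
4. Let any other retained variable keep its odds ratio, interval and cut-off, labelled exploratory and in need of external confirmation.
5. State how correlation is judged and which member of a correlated set is kept, since the error rate depends on it.

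The cost is some wording and one extra column, with no new data. The price in unqualified claims is the power loss shown above, largest for moderate differences; nothing is withheld, because unadjusted results remain. One limit should be stated: the adjustment covers the marginal tests and does not fully correct the multivariable P-values for selection.

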#### Limitations:

First, we will examine patients who had already been diagnosed with the MCA aneurysms. Thus, it cannot be excluded that at early stages of the aneurysm formation, morphometric and hemodynamic parameters of the MCA bifurcation might have been slightly different than they will be at the time of the study. Second, although the MCA aneurysms will be erased from the vascular images before the morphometric analysis, their presence might interfere with the bifurcation geometry. Third, the study might also suffer from a selection bias. Although the participants will be enrolled prospectively, some might be inadvertently excluded due to small size of aneurysms missed on CT scans.

# 8. OUTCOME MEASURES

#### **Primary Outcome Measure:**

1. Computed tomography angiography (CTA) analysis of the cross-sectional area of the MCA bifurcations.

CTA scans in DICOM format will be used to create three-dimensional (3D) models of MCA bifurcation using Mimics Innovation Suite platform (Materialise, Leuven, Belgium). The points including the largest curvature of MCA main trunk and two post-bifurcations branches will be automatically calculated according to the centreline fitted with a computer-aided

design (CAD) tool. In these points the cross-sectional area (mm2) of the MCA trunk and its two post-bifurcation branches will be calculated automatically.

2. Computed tomography angiography (CTA) analysis of the best fit diameter of the MCA bifurcations.

CTA scans in DICOM format will be used to create three-dimensional (3D) models of MCA bifurcation using Mimics Innovation Suite platform (Materialise, Leuven, Belgium). The points including the largest curvature of MCA main trunk and two post-bifurcations branches will be automatically calculated according to the centreline fitted with a computer-aided design (CAD) tool. In these points the best fit diameter (mm) of the MCA trunk and its two post-bifurcation branches will be calculated automatically.

3. Computed tomography angiography (CTA) analysis of the angles between the MCA bifurcations components.

CTA scans in DICOM format will be used to create three-dimensional (3D) models of MCA bifurcation using Mimics Innovation Suite platform (Materialise, Leuven, Belgium). The points of the largest curvature of MCA main trunk and two post-bifurcations branches will be calculated according to the centreline fitted automatically with a computer-aided design (CAD) tool. The centrelines and the largest curvature points will be exported to 3-matic v.9.0 MIS software. Three points of the largest curvatures (the main MCA trunk and two post-bifurcations branches) together with the point of the intersection of both centrelines passing through the main trunk MCA and both branches will determine the arms and the apex of the three angles. The following angle values will be calculated automatically: the angle between the post-bifurcation branches ( $\alpha$  angle) and the angles between the MCA trunk and the larger and the smaller branches ( $\beta$  and  $\gamma$  angle).

4. Pulsatility Index (PI) as calculated from transcranial color-coded sonography (TCCS) blood flow velocities (cm/s)

The assessment of blood flow velocities in both MCAs will be performed by transcranial color-coded sonography (TCCS) using a Vivid 3 Pro (GE Healthcare, Chicago, Illinois, USA) equipped with a multi-frequency transcranial probe (1.5-3.6 MHz). For both MCAs the following will be automatically measured:

- 1. mean blood flow velocity (V) [cm/s]
- 2. peak systolic velocity (Vps) [cm/s]
- end-diastolic velocity (Ved) [cm/s] The velocity measurements will be used to calculate in each vessel the pulsatility index (PI), calculated using the following formula: PI=(Vps-Ved)/V

5. Volume Flow Rate (VFR) as calculated from transcranial color-coded sonography (TCCS) blood flow velocities (cm/s)

The assessment of blood flow velocities in both MCAs will be performed by transcranial color-coded sonography (TCCS) using a Vivid 3 Pro (GE Healthcare, Chicago, Illinois, USA) equipped with a multi-frequency transcranial probe (1.5-3.6 MHz). For both MCAs the following will be automatically measured:

- 1. mean blood flow velocity (V) [cm/s]
- 2. peak systolic velocity (Vps) [cm/s]
- end-diastolic velocity (Ved) [cm/s] The velocity measurements will be used to calculate in each vessel the volume flow rate (VFR) using the following formula: VFR=V\*p, where p - a cross-sectional area of the main MCA trunk, calculated from the morphometric analysis

# 9. ELIGIBILITY

Sex/Gender: male and female, a minimum of 75 cases and 75 age- and sex-matched controls Age Limits: <75 years

**Eligibility Criteria:** The study will include patients (further referred to as cases) with unruptured MCA aneurysm diagnosed on three-dimensional computed tomography angiography (3D CTA).

Case inclusion criteria

- all patients with unruptured MCA aged between 18-75 years

Case exclusion criteria

- refusal to participate in the study
- inability to give informed consent
- presence of multiple cerebral aneurysms

- presence of pathologies, other than MCA aneurysm, in the central nervous system that could have a potential effect on cerebral blood flow (e.g. ischemic stroke, intracerebral or subarachnoid haemorrhage)
- severe systemic disorders (e.g. neoplastic disease)
- severe heart failure or multi-organ failure
- hemodynamically significant internal carotid artery stenosis
- pregnancy
- family history of cerebral aneurysms.

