#### Morphometric Analysis of MCA Bifurcations:

3D CTA scans data in DICOM format will be transferred to Mimics Innovation Suite (MIS) platform (Materialise, Leuven, Belgium). Image segmentation and creation of 3D models will be carried out with Mimics v.17.0 MIS software (Materialise, Leuven, Belgium). The process of segmentation will include main trunks of the MCA and the post-bifurcation branches. Trifurcations of the main MCA trunk will be excluded from the morphometric analysis. MCA bifurcations from the aneurysm patients will be divided into two groups: the An group with aneurysmal MCA bifurcations and the non-An group with contralateral non-aneurysmal MCA bifurcations. Also, MCA bifurcations from the controls will be divided into two groups: R-MCA group with bifurcations of the right MCA and the L-MCA group with bifurcations of the left MCA. Before the morphometric calculations, the MCA aneurysms in the An group will be digitally erased using the Mimics software. After completing the 3D model, the vessel centreline will be fitted automatically with a computer-aided design (CAD) tool. The other parameters: tortuosity, the largest curvature of MCA main trunk and the largest curvatures of the two post-bifurcations branches will be calculated automatically according to the centreline. The points of the largest curvature will be set as close to the bifurcation as possible, but in a distance longer than 5 mm. Based on these points, the cross-sectional area and the best fit diameter of the MCA trunk (p0 and d0, respectively) and its two postbifurcation branches (p1, d1 and p2, d2 for the larger and smaller branch, respectively) will be estimated. The best fit diameters will be then used to calculate the radii of the main MCA trunk  $(r_0)$  and its branches  $(r_1 \text{ and } r_2 \text{ for the larger and smaller branch, respectively})$  using the following formula:

$$r=d/2$$
 (1)

where r - radius and d - the best fit diameter. The radii will be used to calculate two ratios describing the bifurcation asymmetry:

asymmetry ratio=
$$r_2^2 r_1^{-2}$$
 (2)

and

area ratio=
$$(r_1^2 + r_2^2)r_0^{-2}$$
 (3)

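### Controls are matched on age and sex, but no case-control test or model uses the matching or includes age and sex, so results for age- or sex-linked predictors can be distorted.

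*Combined protocol and SAP*

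**What the plan says.** Section 9 (Eligibility) plans "a minimum of 75 cases and 75 age- and sex-matched controls". It does not say whether matching is by individual pairs or by frequency, and it gives no age caliper. The subsection on recruiting controls does not mention matching.

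The Analysis Plan in section 7 introduces its candidates with "The following variables will be evaluated as potential risk factors for MCA aneurysm formation". The list has 15 items: six radii and areas, tortuosity, two ratios, three angles, mean velocity, volume flow rate and pulsatility index. Age and sex are not among them.

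On testing it says "significance of intergroup and intragroup differences will be verified with Mann-Whitney" and, for the intragroup part, the Wilcoxon signed-rank test. The only paired test is therefore the within-person one. Next, "All morphological and hemodynamic parameters shown to differ significantly between the study groups will be subjected to logistic regression analysis with stepwise addition mode". Variables with P<0.1 on univariate analysis, other than mutually correlated ones, "will be included in multivariate logistic regression model, to identify independent predictors of MCA aneurysm". Finally, "The independent predictors of MCA aneurysm will be subjected to receiver operating characteristic (ROC) analysis to identify their cut-off values".

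No conditional model, matched-set term or stratification appears. The Limitations subsection does not mention matching, age or sex.

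**The concern.** In a case-control study, matching does not remove confounding by itself. It selects controls on the matching factors, and the analysis then has to take those factors into account. If they are left out, what happens depends on how close the matching was.

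- **Close matching.** A predictor linked to age or sex varies together with them in both groups. The unadjusted odds ratio is pulled toward 1, and the test is conservative because it uses too large a variance.
- **Loose matching.** A remaining age or sex difference leaks into the comparison. It can push the odds ratio either way, and a null variable can be declared significant too often.

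The plan does not let a reader tell which situation applies. The stake is more than precision: a candidate must pass two significance screens before it receives a multivariable odds ratio or an ROC cut-off. Screening on a test that ignores the matching can remove a real predictor altogether or admit a null one.

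**Working it through.** **Inputs from the documents.** At least 75 cases and 75 controls, matched on age and sex (section 9); ages 18-75; significance at 0.05 (Analysis Plan; two-sided assumed). The 75 per group cannot be reproduced, because no power, effect size or SD is given.

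**Assumed inputs.** R2 is the share of a predictor's variance explained by age and sex; the documents give no value, so 0 to 0.3 is shown. The predictor is normal, odds ratios are per SD, and each person contributes one bifurcation. The standard error of a standardised mean difference is sqrt(2/75) = 0.163.

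**Close matching.** Before any screening:
- unadjusted log OR = (1 - R2) × ln(OR)
- unadjusted type I error = 2 × [1 - Φ(1.96/sqrt(1 - R2))]
- unadjusted power ≈ Φ([(1 - R2) ln(OR)/0.163 - 1.96]/sqrt(1 - R2))
- adjusted power ≈ Φ(sqrt(1 - R2) ln(OR)/0.163 - 1.96)

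| R2 | True OR 2.0 reads as | Type I error, unadjusted | Power at OR 1.5, unadjusted | Power at OR 1.5, adjusted |
|---|---|---|---|---|
| 0 | 2.00 | 5.0% | 70% | 70% |
| 0.1 | 1.87 | 3.9% | 61% | 65% |
| 0.2 | 1.74 | 2.8% | 51% | 60% |
| 0.3 | 1.62 | 1.9% | 40% | 55% |

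Example at R2 = 0.2: 0.8 × ln 2 = 0.555, and exp(0.555) = 1.74. Simulations of frequency-matched samples and exact pairs gave power of 68-70%, 59-61%, 48-51% and 38-39% unadjusted, against 68-70%, 63-65%, 58-60% and 53-55% adjusted. The loss is about 0, 5, 10 and 15 points.

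**Loose matching.** Let g be the remaining mean age gap in SD, with age carrying half of R2. Then the crude log OR = (1 - R2) ln(OR) + g × sqrt(R2/2). For a null predictor:

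| R2 | OR at g = 0.3 | Type I error at g = 0.3 | Type I error at g = 0.5 |
|---|---|---|---|
| 0.1 | 1.07 | 5.8% | 9.2% |
| 0.2 | 1.10 | 6.4% | 13.4% |
| 0.3 | 1.12 | 6.9% | 17.8% |

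Example at R2 = 0.2, g = 0.5: shift 0.5 × 0.316 = 0.158; 0.158/0.163 = 0.968; (1.96 - 0.968)/sqrt(0.8) = 1.11, giving 13.4% with the small opposite tail. In simulation the adjusted test held 4.3-5.4% at these gaps. The unadjusted test turns from conservative to anti-conservative at a gap of 0.23-0.24 SD. If ages were uniform on 18-75, the SD would be 57/sqrt(12) = 16.5 years, so this is about 4 years, and 0.5 SD is about 8 years. A true OR of 1.5 at R2 = 0.2 reads as 1.26 or 1.52 for gaps of -0.3 or +0.3 SD.

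**After the planned screens.** Odds ratios reported only if significant are also inflated by selection. Under close matching with a true OR of 1.5, the median unadjusted OR among retained predictors was 1.62, 1.59, 1.56 and 1.52 at R2 = 0, 0.1, 0.2 and 0.3. With adjusted screening it was 1.61, 1.65, 1.69 and 1.72. With a true OR of 2.0 the retained medians at R2 = 0.1 to 0.3 were 1.90, 1.77 and 1.67 unadjusted, against 2.04-2.06 adjusted.

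**Unit of analysis.** The morphometric section says "MCA bifurcations from the controls will be divided into two groups: R-MCA group with bifurcations of the right MCA and the L-MCA group" for the left side. If both control sides entered as independent rows (75 v 150, assumed within-person correlation 0.7), simulated type I error with adjustment was 7.4-8.1%. Person-clustered standard errors gave 4.9-5.7%.

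**The case against.** The strongest objection concerns size. Nothing in the documents links any MCA variable to age or sex. A reader might infer such a link from the title of reference 7, but that title concerns the basilar bifurcation angle and establishes nothing for the MCA. At R2 = 0 nothing is lost, and at 0.1 the loss is about 5 power points. Under close matching the single-predictor test is conservative and adds no false positives. The higher error rates need an age gap of about 0.5 SD, and a missing caliper is not evidence of one; at 0.3 SD the rate is only about 6-7%. All of this stands and limits the weight of the point.

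A reader might also infer that every retained odds ratio is understated. The planned selection does not support that: at a true OR of 1.5 the retained unadjusted estimates had medians at or above the truth, and adjusted screening moved them further above it. The understatement persisted among retained predictors at 2.0.

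Nor does adjusting the logistic models settle everything. An ROC curve on the raw variable still ignores age and sex, and adjustment does not cure entering two sides per person.

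The gap in the analysis remains. Understating and missing linked predictors matters in a study whose purpose is to find them, and a reader cannot establish how close the matching was.

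**Conclusion.** The concern holds as a mismatch between design and analysis that should be fixed, with medium confidence. For an age- or sex-linked predictor, close matching pulls the unadjusted, unscreened odds ratio toward 1 and costs power; a residual gap can bias it either way and raise type I error above 5%. Multivariable odds ratios can also move either way. The effect is nil without a link, small at R2 = 0.1 and large only near 0.3. These figures rest on assumed R2 values, a normal predictor and one bifurcation per person.

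The documents do not support the stronger claim that the reported odds ratios are wrong in a known direction: for modest effects, selection inflation and the matching bias oppose each other, and the net error can have either sign. The within-patient comparison of aneurysmal and contralateral bifurcations is unaffected.

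**What to change.** In the Analysis Plan:

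1. Force age (continuous) and sex into every univariable and multivariable case-control logistic model, exempt from the stepwise and P<0.1 rules.
2. Base case-control screening on that adjusted test and keep Mann-Whitney as descriptive.
3. Report ROC cut-offs as unadjusted for age and sex, or use an age- and sex-adjusted ROC analysis.
4. Use one bifurcation per person in these models, or person-clustered standard errors.
5. State whether matching was by pairs or frequency, give the caliper, and report the remaining age and sex differences. If individual pairs were kept, conditional logistic regression is an alternative, with age also in the model if matching was loose.

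Leave the within-patient Wilcoxon comparison unchanged.

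**Cost.** Section 2 lists the study as completed, so this is a wording change and a re-analysis. Age and sex should already be held, since they were needed for matching. The models gain two parameters. The screening test becomes parametric, so strongly skewed variables may need a transformation. The plan already checks this: "Normal distribution of the study variables will be verified with Shapiro-Wilk test". In simulation with a strongly skewed predictor (skewness 3.3) and no age or sex link, adjusted power was 56% on the raw scale, 68% for Mann-Whitney and 70% for an adjusted rank-normal score. Adjustment does not remove selection inflation, so retained odds ratios should be presented with that caution.
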